Local implementation strategies: a guide for local facilitators that focuses on environmental implementation strategies. It was developed using results of a national survey of acute surgical teams. It includes a graded strategy system to promote uptake of the education package and to support implementation of its evidence-based recommendations. All participating sites will be asked to report the level of implementation of the proposed strategies.

[figure not shown]
The CLARITY evidence-based education programme

The EBP is an online educational intervention containing six modules:

- 1. Introduction to the anatomy and pathophysiology of appendicitis and how to manage risk which evolves over time
- 2. Discussion on the meaning of evidence and how to use it in clinical practice
- 3. Patient-level risk stratification of appendicitis for RIF pain, focusing on the management of low-risk patients
- 4. Patient-level risk stratification of appendicitis for RIF pain, focusing on the management of medium- and high-risk patients
- 5. Communication with patients and colleagues (implementation)
- 6. Summary of the EBP

Intervention timing

Figure 3: Illustrates the timeline for site recruitment and participation.

Sites will be randomised to either receive the CLARITY intervention or usual care once all site approvals have been confirmed. A minimisation algorithm will be used which will allow for sites to be sequentially randomised once ready. The data collection window will take into account changeover in clinical placements for doctors. If the trial is not completed within a single rotation, doctors who have received the CLARITY package could move from sites which received the intervention to sites which did not receive the intervention, thereby contaminating the results. We will monitor and try to minimise this effect as much as possible.

To ensure that the study is attractive for potential collaborators to participate, all hospitals will have access to the CLARITY accurate-diagnosis package at the end of the trial.

Training platform

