Pilot Trial Outcomes

The outcomes of the pilot trial are:

- 1. The number of sites opened to recruitment within the first four month study period.
- 2. The proportion of patients with complete data collection by the end of the first 4 month study period.
- 3. The proportion of participants completing the CLARITY EBP within the first 4 week training and implementation period.

MAIN TRIAL

Main Trial Design

The CLARITY trial is a multicentre, cluster randomised controlled trial using a hybrid type II implementation effectiveness design. Sites will be randomised using a 1:1 minimisation algorithm.

Main Trial Setting

The study will take place in NHS trusts across the United Kingdom with emergency surgery services. The evidence based programme will be delivered at the hospital-level, with outcomes assessed at the individual patient-level.

Main Trial Time Frame

Each participating hospital will collect data on consecutive patients for 8 weeks. Centres randomised to the intervention arm should aim to have staff trained in the CLARITY EBP, any changes implemented and running within 4 weeks, prior to the launch of data collection. Data on patients presenting or referred with right iliac fossa pain (suspected appendicitis) will then be collected for 8 weeks and used to measure the impact of implementing the CLARITY EBP.

These timeframes have been selected to allow recruitment and data collection to be completed within a single placement rotation of medical staff. This minimises the risk that staff who had completed the CLARITY intervention move to hospitals that have been randomised not to receive the intervention and vice-versa.

Main Trial Cluster Randomisation

Cluster randomisation will be performed at the hospital-level (one hospital is defined as one cluster). The CLARITY package is targeted at healthcare professionals, therefore individual patient-level randomisation would not be appropriate.

A minimisation algorithm will be used at the time of randomisation to ensure that the two groups are balanced for size of hospital and other factors which may influence outcomes (e.g. availability of imaging out of hours). In terms of hospital size, we will minimise based on the total number of beds. A large hospital will be deemed to be 400 beds and over, whereas a small hospital is under 400 beds.

Main Trial Primary Outcome Measure

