In the latter phase of data collection, patients who attended or were admitted to hospital with right iliac fossa pain, including those who did not undergo appendicectomy or were found to have alternative cause for their right iliac fossa pain, will be followed up to a maximum of 30 days (with day 0 being the day of attendance/admission) by a review of their inpatient health records, routine clinic visit letters, and reports for postoperative radiological investigations arranged as part of normal patient care. There will be no additional patient contact (telephone or in-person) beyond what is normal clinical practice at each centre. The study is designed so that existing patient follow-up pathways and health records can be used efficiently, with only data that is routinely collected as part of normal clinical care being captured. Appendicitis is unlikely to spontaneously resolve or recur without treatment (surgery or antibiotics), so 30 days should provide an adequate time frame to capture any complications or readmissions.

The CRF on REDCap has been designed to be straightforward and focuses on pertinent data points. In order to ensure the trial has validity, a minimum threshold of 90% data completion across all included patients will be used. Centres who have 90% or higher data completion rates will be included in the trial analysis and all CLARITY team members will be eligible for co-authorship. Centres with data completion below 90% will not be eligible for co-authorship.

Figure 4: Overview of REDCap data collection forms to be completed for the main CLARITY study.

REDCap forms to complete

SAMPLE SIZE

To detect a 25% reduction in the non-operative admission rate, assuming an intra-cluster correlation (ICC) of 0.06 and an α of 0.05, 40 clusters (20 per arm) of 120 patients would be required — 4800 patients in total. This sample size would provide a power of 0.90. We have been conservative in these estimates and factored in a cluster size variation of 50%.

PROJECTED ACCRUAL

Assuming each of the 40 centres sees 20 patients per week with right iliac fossa pain or suspected appendicitis, each centre should have accrued adequate data within 6 weeks of data collection commencing. The data collection period should run for 8 weeks, so there will be adequate time for centres to accrue cases and achieve the expected sample size.

STATISTICAL ANALYSIS PLAN

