Analyses will be conducted on an intention-to-treat basis (i.e. all patients recorded in the database during the scheduled 8-week recruitment periods will be included). We will compile a full statistical analysis plan prior to data analysis. This trial will be reported according to the CONSORT guidelines, the CONSORT cluster RCT extension and the Standards for Reporting Implementation Studies (StaRI) statement.

Statistical analysis

All analyses will be performed with respect to the clustered nature of the data. Summary data will be tabulated using simple counts and percentages for categorical data. Where continuous data are normally distributed, the mean average will be presented alongside the standard deviation. Where data are not normally distributed, the median average will be presented alongside the 25th and 75th percentiles. Given randomisation, we will not formally test for differences in the characteristics of patients included in different clusters.

All data will be checked and data quality rules will be implemented to ensure data included in analyses are accurate. Missing covariate data will be fully reported and the reason for missingness established. Where possible, centres will be asked to supply the missing data, however, if this is not possible, we will perform multiple imputation when there is a significant amount of missing data (>10%). For missing outcome data, we will perform a best/worst case scenario analysis by imputing missing values with extreme values to assess whether missing outcome data is likely to impact our findings.

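### The 90% data-completion rule implies that some randomised hospitals are left out of the analysis, which conflicts with the protocol's own intention-to-treat definition

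*Protocol*

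**What the plan says.** The protocol's data collection and follow-up section introduces the threshold as a matter of validity: "In order to ensure the trial has validity, a minimum threshold of 90% data completion across all included patients will be used". It continues: "Centres who have 90% or higher data completion rates will be included in the trial analysis", and the same sentence goes on to grant co-authorship to those teams. For the remaining centres it says only this: "Centres with data completion below 90% will not be eligible for co-authorship".

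The statistical analysis plan section of the protocol sets the analysis population by intention to treat and explains what that means: "all patients recorded in the database during the scheduled 8-week recruitment periods will be included". No completeness condition is attached. The statistical analysis subsection then gives rules for missing data. Missing covariates are requested from the centre and, failing that, multiply imputed when more than 10% are missing. For outcomes, "For missing outcome data, we will perform a best/worst case scenario analysis by imputing missing values with extreme values".

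The hospital is the unit of randomisation (cluster randomisation sections, pilot and main trial). On timing, the protocol states: "Sites will be randomised to either receive the CLARITY intervention or usual care once all site approvals have been confirmed". Data collection follows later. The blinding section says that neither the surgical team nor the outcome assessor can be blinded, and that the analysis is done blind to allocation.

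**The concern.** The two sections give different answers to a basic question: which randomised hospitals are in the primary analysis? An SAP written later would have to depart from one of them, so this is not a detail simply left open.

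The choice matters for three reasons.

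- Completion is a characteristic of the whole cluster that is observed after allocation. Selecting clusters on it gives up the protection of randomisation. If completion is related to both arm and outcome, the estimate is biased.
- The threshold refers to data completion in general. A hospital with every non-operative admission recorded could be left out because of gaps in other fields.
- The trial is limited by its number of clusters. The sample size section allows for variation in cluster size but states no allowance for losing whole clusters.

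**Working it through.** **Passages side by side.** Take a hospital that records its patients at 85% completion. Under the intention-to-treat definition its patients are analysed, with gaps handled by the missing-data rules. Under the follow-up section it does not meet the stated condition for inclusion. Both cannot apply.

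**Inputs for power.** From the sample size section: ICC 0.06, m = 120 per cluster, 20 clusters per arm, cluster size variation 50% (taken as CV 0.5), α 0.05 (taken as two-sided), 25% reduction (taken as relative). That section gives no baseline rate. I assume 60%, from the background statement on admitted patients who receive no intervention, so the comparison is 60% v 45%.

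**Reproducing the plan.**

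- Design effect: 1 + ((1 + 0.5²) × 120 − 1) × 0.06 = 1 + 149 × 0.06 = 9.94.
- Individually randomised size for 90% power (normal approximation, pooled variance under the null): 231 per arm.
- Clusters per arm: 231 × 9.94 / 120 = 19.13, rounded up to 20. Total 40 × 120 = 4800, as stated.

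**Power with k clusters per arm.** SE = √{[p₁(1 − p₁) + p₂(1 − p₂)] × 9.94 / (120k)}, where the bracket is 0.24 + 0.2475 = 0.4875. Power comes from a non-central t with 2k − 2 degrees of freedom and non-centrality 0.15 / SE.

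| Clusters in total | SE | 0.15 / SE | Power |
|---|---|---|---|
| 40 | 0.0449 | 3.34 | 0.90 |
| 36 | 0.0474 | 3.17 | 0.87 |
| 32 | 0.0502 | 2.99 | 0.82 |

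The first row agrees with the stated 0.90. The losses of 4 and 8 clusters are illustrative and equal by arm.

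**Sensitivity to the assumed baseline.** With all 40 clusters and the same 25% relative reduction, power is 0.78 at a 50% baseline, 0.84 at 55%, 0.90 at 60% and 0.95 at 65%.

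**Size of a possible bias.** This is illustration only.

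- Simple arithmetic: suppose 4 of 20 hospitals in one arm are left out and their rate differs by 10 points from that of the other 16. The arm mean moves by (4/20) × 10 = 2 points, against a target difference of 15 points.
- Simulation under no true effect (beta-binomial, 60%, ICC 0.06, 20 per arm, cluster-level t-test): suppose each intervention hospital in the third with the highest rates has a 50% chance of being left out. The bias is about −2.9 points and the type I error about 11%. With a 25% chance these are about −1.3 points and 7%.
- If both arms lose hospitals in the same way, there is no bias.

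**The case against.** The best defence is that the protocol never says centres below 90% are excluded. It names only loss of co-authorship, the intention-to-treat statement is explicit, and a full SAP is promised. On that view the threshold is an incentive for data quality. It is true that exclusion is implied rather than stated. But the threshold is justified by the validity of the trial, and inclusion in the analysis is listed as a consequence separate from authorship. If every centre is analysed anyway, that clause does nothing. If authorship was all that was meant, the text still needs correcting.

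Several stronger readings are tempting, but the documents do not support them:

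- *The intervention itself drives completion through champions and weekly contact.* The protocol describes champions at each site and weekly contact for all participating centres. Only the education package and its training are specific to an arm, so differential completion is possible but not shown.
- *Unblinded sites decide who is excluded.* A numerical threshold would decide, and the analysis is to be blind to allocation. What stands is that the people producing the data know the allocation.
- *The rule removes most of the data that imputation is meant for.* The 10% trigger concerns covariates, whereas the 90% threshold is overall completion by centre. One covariate could be 30% missing while every centre passes. The overlap is real, but its extent is unknown.
- *Type I error would be about 11%.* That is a single extreme pattern, confined to one arm. Nothing in the documents links completion to the primary outcome in one arm only.

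It is also fair to say that missing data are actively queried, that the source is routine notes, and that the design section expects at least another 30 sites beyond the roughly 10 in the pilot. Forty clusters is therefore not a ceiling, and few centres may fall below 90%.

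**Conclusion.** The point holds as a conflict over the primary analysis set, and it should be resolved before analysis. The follow-up section makes inclusion conditional on a post-randomisation measure, while the statistical analysis plan section includes everyone recorded. This conclusion rests on the wording alone and on no numerical assumption.

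The main consequence is for validity: the protocol as written allows whole randomised hospitals to be left out. The direction and size of any bias cannot be determined from the documents. The loss of power is secondary. It is about 3 points for 4 clusters lost and 8 points for 8 lost, given the assumed 60% baseline. The protocol gives no expected number of centres below 90%.

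**What to change.** Reword the follow-up section to say that the 90% threshold governs co-authorship and the raising of data queries only. State there that all randomised hospitals, and all their recorded patients, enter the primary analysis, with missing covariates and outcomes handled as the statistical analysis subsection already provides. If a restricted analysis is wanted, present centres at or above 90% as a labelled sensitivity analysis, and report the number of centres below 90% by arm.

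The cost is a sentence or two of protocol text. The downside is more missing data in the primary analysis and wider best/worst-case bounds if some centres complete poorly. Those bounds would then show the uncertainty that leaving these centres out would hide.

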Secondary Outcomes: Safety (including negative appendicectomy, postoperative complication rate, readmission, missed disease).

Sample size: 40 clusters (20 per arm) of 120 patients would be required to detect a 25% reduction in non-operative admission rate (4800 patients in total, power = 0.90, α = 0.05).

Randomisation: Hospitals will be categorised by bed size (<400 or >400 beds) and randomised using a 1:1 minimisation algorithm.

[figure not shown]
Follow up: This will be carried out by reviewing hospital notes 30 days after attendance/admission.

Analysis: Intention to treat, including implementation analyses.

Potential Impact:

- 1. Improved patient care, with a reduction in unnecessary admissions and negative appendectomies.
- 2. Reduction in healthcare costs by preventing unnecessary surgeries.
- 3. More efficient allocation of emergency resources, reducing hospital stays and admissions.

Figure 1: CLARITY trial design

PLAIN LANGUAGE SUMMARY

Appendicitis is a common condition, it is caused by inflammation of a small part of the bowel called the appendix. It does not usually get better by itself and the main treatment is to remove the appendix with an operation. This can then be studied by doctors under the microscope to confirm the diagnosis.

Appendicitis can be challenging to diagnose, as many other conditions can cause similar symptoms. To help make a diagnosis doctors can use blood tests and scans, but how these are used and the decisions made based on results is different across the country. This has led to many patients receiving an incorrect diagnosis and treatment. Often many patients are admitted to hospital for suspected appendicitis but are monitored and do not receive any treatment before they are discharged. Furthermore, some of those admitted go on to have an unnecessary surgery to remove a healthy appendix. In the UK, around 20% of patients who have an operation to remove an inflamed appendix are found not to have appendicitis. Therefore, these people will have undergone an operation that they did not require. This rate of unnecessary operations is three times higher than other European Countries.

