CLARITY is a study which aims to improve patient care pathways and to ensure that patients with suspected appendicitis receive the appropriate care that they need. We will do this by trying to reduce unnecessary admissions for appendicitis in the United Kingdom. CLARITY will test whether educating doctors who diagnose and treat appendicitis prompts them to use the best evidence strategies to diagnose appendicitis correctly. In turn this may enable doctors to reach the correct diagnosis earlier and to use admissions or surgery in patients that require them. As this trial is testing an intervention on doctors, rather than individuals with appendicitis, there will be no change to the care received and no extra appointments or surveys to complete for most people included in the study. The CLARITY trial is being funded by the University of Birmingham. We will share the results with patients and doctors through social media communications, presentations at scientific conferences and publishing our work.

BACKGROUND AND RATIONALE

Need for research in acute appendicitis

Acute appendicitis is one of the most common surgical emergencies managed by general surgical departments worldwide. In the UK, approximately 50,000 appendicectomies are performed every year.[1] It is generally considered the gold standard for the treatment of appendicitis. However, there is growing concern that a significant proportion of patients who are admitted to hospital or undergo surgery for appendicitis have a histologically normal appendix.

This is because appendicitis is often difficult to diagnose accurately. Typically, an individual with appendicitis presents with abdominal pain that localises to the right iliac fossa. However, some patients may have an atypical presentation or symptoms that overlap with an alternate diagnosis (for example, a ureteric stone, a urinary tract infection or problems affecting the fallopian tubes or ovaries).

Unnecessary admissions and operations are accompanied with significant risks and costs for the health service. Around 60% of patients admitted for suspected appendicitis are monitored and do not receive an intervention.[2-3] This signifies suboptimal care and places a significant burden on the health service. It is thought that improved diagnostic processes, such as risk stratification, imaging and redirection through ambulatory services, could improve right iliac fossa care pathways.

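### The power of 0.90 needs a control rate near 60%, a figure the protocol gives only for admitted patients, while cluster size and analysis set count all attendees

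*Protocol*

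**What the plan says.** The Sample size section sets the target and inputs: "To detect a 25% reduction in the non-operative admission rate, assuming an intra-cluster correlation (ICC) of 0.06 and an α of 0.05". It concludes that "40 clusters (20 per arm) of 120 patients would be required" and adds "This sample size would provide a power of 0.90". It describes the estimates as conservative and says that a 50% variation in cluster size is included. The Summary repeats the claim as "4800 patients in total, power = 0.90". Neither place gives a control-arm NOAR, says whether 25% is relative or absolute, or says whether α is two-sided.

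The only figure elsewhere in the protocol that could serve as a control rate is in the background, under the need for research in acute appendicitis: "Around 60% of patients admitted for suspected appendicitis are monitored and do not receive an intervention". Its denominator is patients admitted.

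The cluster size has a different denominator. Projected accrual reads "Assuming each of the 40 centres sees 20 patients per week with right iliac fossa pain or suspected appendicitis", which gives 120 in six weeks. Patient identification states that neither an overnight stay nor admission is required for inclusion. The Statistical analysis plan section analyses every patient recorded in the eight-week window. The Main Trial Primary Outcome Measure words NOAR so that it can be read as a proportion of those admitted overnight or of all patients with right iliac fossa pain.

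**The concern.** The stated power appears to combine an event rate among admitted patients with a count of attendees. These have the same denominator only if practically everyone who attends is admitted, which the eligibility text does not assume. If NOAR is analysed over all recorded patients, the control rate is lower than 60%, a 25% relative reduction is a smaller absolute difference, and power falls.

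The headline figure then matters in two ways. The trial is justified by 0.90 and its assumptions are called conservative. A non-significant result could also be read as stronger evidence against a 25% reduction than the design supports. Reporting confidence intervals, which the protocol promises, limits this but does not correct the stated power.

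**Working it through.** **Inputs.** From Sample size: 20 clusters per arm, m = 120, ICC = 0.06, cluster size CV = 0.50, α = 0.05, 25% reduction. From the background: about 60% of admitted patients have no intervention. From Projected accrual: 20 attendees a week, so 120 in 6 weeks and 160 in 8. Assumed here: two-sided test, relative reduction, and the share of attendees admitted overnight, which the protocol does not give.

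**Reproducing 0.90.**
- Design effect = 1 + [(1 + CV²)m − 1] × ICC = 1 + (1.25 × 120 − 1) × 0.06 = 9.94.
- Effective n per arm = 20 × 120 / 9.94 = 241.4.
- Noncentrality λ = (p1 − p2) / √{[p1(1 − p1) + p2(1 − p2)] / n}. For 60% versus 45%: 0.15 / √(0.4875 / 241.4) = 3.338.
- Power from the noncentral t with 40 − 2 = 38 df (critical value 2.024) = **0.902**. The normal approximation with pooled null variance gives 0.912.
- The baseline that returns exactly 0.90 is 59.8% (t) or 58.7% (normal).

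Departing from the stated or usual inputs changes that baseline. Ignoring cluster size variation it is about 54% (t), and with one-sided α about 53% (normal). A 25-point absolute reduction would have power above 0.999, so the relative reading is the one that fits 0.90.

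**All-attendee denominator.** Control rate = 0.60 × admitted share; intervention rate = 0.75 × that.

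| Share admitted (assumed) | Control vs intervention | Power, 120 per site | Power, 160 per site |
|---|---|---|---|
| 60% | 36.0% vs 27.0% | 0.55 | 0.56 |
| 70% | 42.0% vs 31.5% | 0.65 | 0.66 |
| 80% | 48.0% vs 36.0% | 0.75 | 0.76 |
| 90% | 54.0% vs 40.5% | 0.83 | 0.84 |
| 95% | 57.0% vs 42.8% | 0.87 | 0.88 |

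The full eight weeks adds only about 0.01 because the ICC dominates: at m = 160 the design effect is 1 + (1.25 × 160 − 1) × 0.06 = 12.94, and effective n is 3200 / 12.94 = 247, against 241. The relative reduction detectable with power 0.90 at 120 per site is about 38% for a 36% baseline, 31% for 48% and 28% for 54%.

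**Admitted-patient denominator.** The rates stay at 60% versus 45% and only the cluster size shrinks, to 120 × admitted share. At 60, 70, 80 and 90% admitted, m is 72, 84, 96 and 108, and power is 0.884, 0.890, 0.895 and 0.899.

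**What that target implies.** An avoided non-operative admission leaves both numerator and denominator. Per 100 admitted, with 40 operations unchanged, reaching 45% needs 40 × 0.45 / 0.55 = 32.7 non-operative admissions instead of 60, a cut of 45%. A 25% cut in their number leaves 45 of 85, or 52.9%; power for 60% versus 52.9% is about 0.32 to 0.33 at 60 to 90% admitted.

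**The case against.** The strongest reply is that the target is a reduction in a rate, and the outcome wording allows that rate to be a proportion of those admitted overnight. On that reading 60% versus 45% is the right contrast, and power stays within two points of 0.90 at every admitted share from 60 to 90%. This stands. A reader might infer that the design cannot deliver 0.90 on any reading of the outcome; the documents do not support that. The power of 0.32 to 0.33 belongs to a different target, a cut in the number of non-operative admissions with operations unchanged, which the Sample size section does not state. It shows how demanding the admitted-patient target is, not that the stated power is miscalculated for it.

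Two further points stand in part. The protocol never says that 60% was used, and the background figure concerns patients without an intervention, which is not quite the same as without an operation. The match at 0.902 makes 60% likely, not proven. The admitted share is also unknown, so the shortfall over all attendees is a range and is small if nearly all are admitted.

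The reply does not settle the matter, because the all-attendee reading is better supported. All recorded patients are analysed, the outcome section expresses the necessary non-operative cases as about 3% of all referrals with right iliac fossa pain, and the aim is to avoid admissions, so patients who avoid one belong in the denominator. Nor can this be left to a later analysis plan: the protocol itself fixes the sample size and states its power.

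**Conclusion.** The concern holds conditionally. With a two-sided test of a relative reduction and the stated ICC and cluster size variation, 0.90 requires a control NOAR near 60%. The protocol supports that figure only for admitted patients, while it sizes clusters by attendees and analyses all of them. On the all-attendee denominator, power for a 25% relative reduction is about 0.55 to 0.87 for an admitted share of 60 to 95%. On the admitted-patient denominator, with 25% meaning a relative fall in that proportion, the stated power is essentially right at 0.88 to 0.90, but for a target equivalent to about 45% fewer non-operative admissions if operations are unchanged. Confidence is moderate: the mismatch of denominators is in the text, but the size of the shortfall rests on an admitted share that the protocol does not give.

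**What to change.** - State one denominator for NOAR, identically in the Main Trial Primary Outcome Measure, Sample size and Statistical analysis plan sections. All eligible attendees fits the analysis set and the aim.
- In Sample size, give the control NOAR on that denominator with its source, and say that 25% is a relative reduction and α is two-sided, if so intended.
- Restate the power of 40 clusters of 120 over a plausible range of control rates, with the relative reduction detectable at 0.90 for each. If all attendees are chosen, the table above can serve until the sponsor supplies the admitted share.
- Correct the 0.90 in the Summary to match, and reconsider calling the estimates conservative.

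The cost is a protocol amendment to wording and a less favourable stated power. No additional patients, sites or data collection are needed.
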